6.1.3.1 Elevation of Creatine Kinase (CK)

If CK is > 5x ULN, CK must be retested before IP is administered. In addition, investigators will ask study subjects to promptly report muscle pain, cramps, or weakness especially if accompanied by malaise or fever. If such symptoms occur and no scheduled study laboratory assessments are performed, the subject's CK levels should be measured by unscheduled assessment. If CK is > 5x ULN, the subject must be instructed as soon as possible to discontinue statin, other applicable lipid background therapy, and IP and CK must be retested before statin, other lipid background therapy, and/or IP (AMG 145) administration can be continued. A sample for urinalysis must be collected and sent to the central laboratory if CK is elevated > 10x ULN on retest as per table below.

The following rules apply for scheduled laboratory assessments and for unscheduled CK measurements:

CK at scheduled or unscheduled visit	CK on retest	Investigational Product and/or Statin Administration
> 5x ULN	> 10x ULN	Discontinue both statin and IP ^a . Collect urine sample for urinalysis. Contact Amgen Medical Monitor.
	> 5x to ≤ 10x ULN	Discontinue statin and retest CK before administration. Consider continuing IP if alternative explanation.
	≤ 5x ULN	Consider continuing statin and IP

^a CK elevations > 10x ULN that have been confirmed to be secondary to myocardial infarction do not require discontinuation of IP

If muscular symptoms are severe and cause daily discomfort, even if the CK levels are elevated to ≤ 5x ULN, reduction of statin dose, discontinuation of statin, or introduction of an alternative statin may be considered at the lowest dose and with close monitoring.

6.1.3.2 Elevation of Liver Function Tests

Subjects with abnormal hepatic laboratory values (eg, alkaline phosphatase [ALP], AST, ALT, total bilirubin [TBL] or signs/symptoms of hepatitis may meet the criteria for withholding of IP, statin, and other applicable lipid background therapy. If the subject

experiences an ALT or AST > 3x ULN, then they must be followed as detailed under section on close observation in [Appendix B](#).

IP, statin and other applicable lipid background therapy must be discontinued and the subject should be followed according to the recommendations in [Appendix B](#) (Additional Safety Assessment Information) for possible drug-induced liver injury (DILI), if ALL of the criteria below are met:

- TBL \geq 2x ULN
- AND **increased** AST or ALT > 3x ULN if **baseline values were less than the ULN**
- AND **ALP < 2x ULN**
- **AND** no other cause for the combination of **the above** laboratory abnormalities is immediately apparent; important **alternative** causes for abnormal AST/ALT **and/or** TBL values include, but are not limited to:
 - Obstructive gall bladder or bile duct disease
 - Viral or alcoholic hepatitis (eg, Hepatitis A/B/C/D/E, Epstein-Barr Virus, cytomegalovirus, Herpes Simplex Virus, Varicella, etc)
 - Progression of malignancy involving the liver (note that metastatic disease to the liver, by itself, should not be used as an explanation for significant AST/ALT elevations)
 - Hypoxic or ischemic hepatopathy or congestive hepatopathy in association with significant right-sided heart failure
 - Concomitant administration of other hepatotoxins, including drugs that inhibit bilirubin glucuronidation (eg, indinavir, atazanavir, irinotecan) or herbal or dietary supplements
 - Heritable disorders causing impaired glucuronidation (eg, Gilbert's Syndrome); alpha-one antitrypsin deficiency
 - Autoimmune hepatitis
 - Nonalcoholic steatohepatitis (NASH) or other "fatty liver disease"

IP, statin, and other applicable lipid background therapy should also be withheld and the subject should be evaluated for Drug Induced Liver Injury (DILI) if ANY of the following criteria are met:

- AST or ALT > 8x ULN at any time
- AST or ALT > 5x ULN but < 8x ULN for \geq 2 weeks
- TBL > 3x ULN at any time
- ALP > 8x ULN at any time
- Clinical signs or symptoms that are, in the opinion of the investigator, consistent with hepatitis (such as right upper quadrant pain/tenderness, fever, nausea, vomiting, jaundice, rash or eosinophilia > 5%). If such signs or symptoms are coupled with ALT or AST elevations > 3x ULN, IP should be withheld.

If IP, statin, and other lipid background therapy is withheld due to any of the conditions above, the subject should be followed according to recommendations in [Appendix B](#) for possible DILI.

6.1.4 Criteria for Rechallenge After Withholding or Discontinuation of IP (AMG 145), Statin and Other Applicable Lipid Background Therapy

The decision to rechallenge the subject after therapy changes due to CK elevation or elevation of liver function tests should be discussed and agreed unanimously upon by the subject, Investigator, and Amgen.

If signs or symptoms recur with rechallenge of IP, then IP should be permanently discontinued. If signs or symptoms recur with rechallenge of statin background therapy, the statin may be substituted by another statin in consultation with the Amgen medical monitor, if possible, or the statin therapy may be discontinued. If signs or symptoms recur with rechallenge of other applicable lipid background therapy, this therapy may be discontinued.

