4.2 Exclusion Criteria

All subjects will be ineligible for the study if they fulfill any of the following criteria:

- 4.2.1 Female subject who has either (1) not used an acceptable method(s) of birth control for at least 1 month prior to screening or (2) is not willing to use such a method during treatment with AMG 145 (IP) and for an additional 15 weeks after the end of treatment with AMG 145 (IP) unless subject is sterilized or postmenopausal;
- Menopause is defined as 12 months of spontaneous and continuous amenorrhea in a female \geq 55 years old or 12 months of spontaneous and continuous amenorrhea with a follicle-stimulating hormone level $>$ 40 IU/L (or according to the definition of "postmenopausal range" for the laboratory involved) in a female $<$ 55 years old unless the subject has undergone bilateral oophorectomy
 - Acceptable methods of preventing pregnancy include sexual abstinence, surgical contraceptive methods (vasectomy or bilateral tubal ligation), use of hormonal birth control methods (pills, shots, implants or patches), intrauterine devices (IUDs), or two (2) barrier methods (each partner must use one barrier method) with spermicide – males must use a condom with spermicide; females must choose either a Diaphragm with spermicide, OR or Cervical cap with spermicide, OR Contraceptive sponge with spermicide.
- 4.2.2 Subject is pregnant or breastfeeding, or planning to become pregnant or breastfeed during treatment with AMG 145 (IP) and for an additional 15 weeks after the end of treatment with AMG 145 (IP)
- 4.2.3 Unreliability as a study participant based on the investigator's (or designee's) knowledge of the subject (eg, inability or unwillingness to adhere to the protocol)
- 4.2.4 Experienced a treatment related serious adverse event that led to IP discontinuation in the AMG 145 parent protocol
- 4.2.5 Disorder that would interfere with understanding and giving informed consent or compliance with protocol requirements
- 4.2.6 Have an unstable medical condition, in the judgment of the investigator.
- 4.2.7 Currently enrolled in another investigational device or drug study, or less than 30 days since ending another investigational device or drug study(s), or receiving other investigational agent(s).

In addition, all subjects that undergo screening procedures will be ineligible for the study if they fulfill any of the following criteria:

- 4.2.8 Use of Mipomersen or Lomitapide within 5 months of screening

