- 4.2.9 Subject has taken a cholesterylester transfer protein (CETP) inhibitor in the last 12 months prior to LDL-C screening, such as: anacetrapib, dalcetrapib or evacetrapib
- 4.2.10 NYHA III or IV heart failure, or last known left ventricular ejection fraction $<$ 30%

- 4.2.11 Uncontrolled serious cardiac arrhythmia defined as recurrent and highly symptomatic ventricular tachycardia, atrial fibrillation with rapid ventricular response, or supraventricular tachycardia that are not controlled by medications, in the past 3 months prior to screening
- 4.2.12 Uncontrolled hypertension defined as sitting systolic **BP** (SBP) > 180 mmHg or diastolic BP (DBP) > 110 mmHg, confirmed with repeat measurement
- 4.2.13 Subject requires uptitration of their current statin dose within 4 weeks of screening (these subjects can be uptitrated and rescreened one month later)
- 4.2.14 Moderate to severe renal dysfunction, defined as an estimated glomerular filtration rate (eGFR) < 30 ml/min/1.73m² at screening
- 4.2.15 Active liver disease or hepatic dysfunction, defined as aspartate aminotransferase (AST) or alanine aminotransferase (ALT) > 3 times the **upper limit of normal (ULN)** as determined by central laboratory analysis at screening
- 4.2.16 Unexplained CK > 5 times the ULN at screening, confirmed by a repeat measurement at least 1 week apart
- 4.2.17 Known active infection or major hematologic, renal, metabolic, gastrointestinal or endocrine dysfunction in the judgment of the investigator
- 4.2.18 Diagnosis of deep vein thrombosis or pulmonary embolism within 3 months prior to screening
- 4.2.19 History of malignancy (except non-melanoma skin cancers, cervical in-situ carcinoma, breast ductal carcinoma in situ, or stage 1 prostate carcinoma) in the last 5 years
- 4.2.20 Subject has previously received a non-AMG 145 investigational therapy to inhibit PCSK9
- 4.2.21 Currently enrolled in a non-AMG 145 investigational device or drug study, or less than 30 days since ending a non-AMG 145 investigational device or drug study(s), or receiving other investigational agent(s)
- 4.2.22 Known sensitivity to any of the products to be administered during dosing

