7. STUDY PROCEDURES

This will be a multicenter, open-label study to assess the long-term safety, tolerability, and efficacy of AMG 145. For the purpose of this study, a month is defined as 4 weeks and a quarter is defined as 12 weeks.

Subjects that fall within a 1 month window of completing a qualifying parent study do not require screening procedures to be performed; they may be enrolled into the study directly, as outlined in [Section 7.1.2](#). All other subjects must go through the study screening procedures as outlines in [Section 7.1.1](#).

Written informed consent must be obtained and will be implemented before protocol specific procedures are carried out. The risks and benefits of participating in the study will be verbally explained to each potential subject prior to entering into the study. The procedures to be performed at each clinic visit are described below and are summarized in [Appendix A](#). Subjects must be fasting for ≥ 9 hours before each study visit where labs are collected. IP should not be administered until all study procedures are completed at each visit. Blood draws for subjects on apheresis (main study and sub-study) will need to occur both before and after apheresis

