Appendix B. Additional Safety Assessment Information

Adverse Event Toxicity Grading Scale

Refer to the NCI Common Terminology Criteria for AEs (CTCAE) Version 4.0 for AE grading and information. The CTCAE is available at the following link:

http://ctep.cancer.gov/protocolDevelopment/electronic_applications/ctc.htm.

When an AE cannot be graded by CTCAE v4.0 the following severity grade may be used:

Grade	Amgen Standard Adverse Event Severity Scoring System
1	MILD: Aware of sign or symptom, but easily tolerated
2	MODERATE: Discomfort enough to cause interference with usual activity
3	SEVERE: Incapacitating with inability to work or do usual activity
4	LIFE-THREATENING: Refers to an event in which the patient was, in the view of the investigator, at risk of death at the time of the event. (This category is not to be used for an event that hypothetically might have caused death if it were more severe.)
5	FATAL

Drug-induced Liver Injury Reporting & Additional Assessments

Reporting

To facilitate appropriate monitoring for signals of DILI, cases of concurrent AST/ALT and TBL elevation according to the criteria specified in [Section 6.1.3.2](#) (3x ULN for AST/ALT, 2x ULN for TBL, and **ALP < 2x ULN**) require the following:

- The event should be reported to Amgen as a serious adverse event within 24 hours of discovery or notification of the event (ie, before additional etiologic investigations have been concluded)
- The appropriate eCRF (eg, adverse event eCRF) that captures information necessary to facilitate the evaluation of treatment-emergent liver abnormalities should be completed.

Other events of hepatotoxicity and potential DILI should be reported as serious adverse events if they meet the criteria for a serious adverse event defined in [Section 9.2.1](#).

Additional Clinical Assessments and Observation

All subjects in whom IP and/or background lipid therapy is withheld due to potential DILI or who experience AST/ALT elevations $>3x$ ULN should undergo a period of “close observation” until abnormalities return to normal or to the subject’s baseline levels.

Assessments that should be performed during this period include:

- Repeat liver chemistries within 24-48 hours (ALT, AST, ALP, TBL); in cases of TBL $\geq 2x$ ULN, **ALP $< 2x$ ULN**, or AST/ALT much greater than $3x$ ULN, retesting should be performed within 24 hours

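### The mandatory combined liver stop in Protocol 6.1.3.2 has no AST/ALT criterion for a baseline at or above ULN, and Appendix B restates the rule without that limit

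*Protocol*

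**What the plan says.** **The combined rule.** Protocol 6.1.3.2 lists four conditions that must all hold before IP, statin and other lipid background therapy must be discontinued: TBL at least 2x ULN; increased AST or ALT above 3x ULN if "baseline values were less than the ULN"; ALP below 2x ULN; and no other apparent cause for the combination. No AST/ALT condition follows for a baseline at or above ULN. The Amendment 6 description of changes gives the same new wording with no second limb, so nothing was lost in the text extraction.

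**Who can enter.** Exclusion 4.2.15 removes subjects with AST or "alanine aminotransferase (ALT) > 3 times the" ULN. It belongs to a list under which "all subjects that undergo screening procedures will be ineligible for the study if they fulfill any of the following criteria". Section 7 says that subjects within 1 month of completing a qualifying parent study "do not require screening procedures to be performed; they may be enrolled into the study directly".

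**What else protects the subject.** Under 6.1.3.2, a subject who "experiences an ALT or AST > 3x ULN, then they must be followed as detailed under section on close observation in" Appendix B. A second list in the same section, any one item of which is enough, covers AST/ALT above 8x ULN, AST/ALT above 5x but below 8x for at least 2 weeks, TBL above 3x, ALP above 8x, and hepatitis signs or symptoms. On the last item it adds: "If such signs or symptoms are coupled with ALT or AST elevations > 3x ULN, IP should be withheld". Section 6.1.3 makes stopping compulsory whenever a withholding criterion is met.

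**The restatement.** For 24-hour SAE reporting, Appendix B refers back to 6.1.3.2 and summarises its criteria as "3x ULN for AST/ALT, 2x ULN for TBL" and ALP below 2x ULN, with no baseline condition.

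**The concern.** A mandatory stop should give one answer for every subject who can be enrolled. Here the enzyme limb is conditional on a normal baseline, while eligibility allows a raised one. A raised baseline is foreseeable: non-parent subjects enter on lipid-lowering therapy, and 6.1.3 itself notes that fenofibrate, ezetimibe or niacin can raise liver tests.

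At stake is the pattern that the combined rule is meant to catch, a concurrent rise in transaminases and bilirubin without cholestasis. A site following 6.1.3.2 as written may continue treatment. A site taking its threshold from Appendix B would stop for the same laboratory values.

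**Working it through.** The plan gives no figure to reproduce here, so the check is of the rule's logic. All values are multiples of ULN. Let b be the baseline of the enzyme, E its on-study value, and assume no other apparent cause.

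**Formulas**

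- Literal 6.1.3.2: TBL ≥ 2, and (b < 1 and E > 3), and ALP < 2.
- Unqualified, as in Appendix B: TBL ≥ 2, and E > 3, and ALP < 2.
- Any-one list (6.1.3.2): E > 8; or 5 < E < 8 for at least 2 weeks; or TBL > 3; or ALP > 8; or hepatitis signs.

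**Eligibility.** Exclusion 4.2.15 applies above 3x ULN, so screened subjects may have b from 1 to 3. Direct rollovers have no numeric AST/ALT limit in this protocol. Their parent-study limits are not in the documents, and exclusion 4.2.6 (unstable medical condition) still applies to them.

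**Illustrative asymptomatic cases**

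| b | E | TBL | ALP | Literal | Unqualified | Any-one list |
|---|---|---|---|---|---|---|
| 0.9 | 4 | 2.5 | 1 | stop | stop | not met |
| 1.5 | 4 | 2.5 | 1 | no stop | stop | not met |
| 2.5 | 4 | 2.5 | 1 | no stop | stop | not met |
| 1.5 | 6 (under 2 weeks) | 2.5 | 1.2 | no stop | stop | not met |
| 1.5 | 9 | 2.5 | 1 | no stop | stop | met |
| 1.5 | 4 | 3.5 | 1 | no stop | stop | met |
| 1.5 | 4 | 2.5 | 3 | no stop | no stop | not met |

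The first two rows have the same on-study values and differ only in baseline. The last row misses both forms of the rule because of ALP; it would do so at any baseline and is not part of this point.

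**The gap.** The two forms disagree, with the any-one list silent, when all of these hold:

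- b ≥ 1;
- 2 ≤ TBL ≤ 3 and ALP < 2;
- no hepatitis signs and no other apparent cause;
- 3 < E ≤ 5 for any duration, or 5 < E < 8 for under 2 weeks, or E exactly 8 (the list uses above 8 and below 8).

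**Effect of removing the condition.** The fold-rise at which E reaches 3x ULN is 3/b, and the limb is met just above it: 3/1 = 3.0; 3/1.5 = 2.0; 3/2 = 1.5; 3/2.5 = 1.2.

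**The case against.** Much of the case on the other side stands.

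- **Intent is visible.** Appendix B contains the only restatement of the criteria, and it carries no baseline condition. That favours above 3x ULN for everyone. But it governs SAE reporting, points back to 6.1.3.2 and does not amend the stop rule.
- **The backstops are strong.** Section 6.1.3 makes the any-one list compulsory when met and requires laboratory review before the next dose. Close observation under Appendix B brings a retest within 24 hours at TBL of 2x ULN or more, at least twice-weekly monitoring and a specialist consult. Section 9.1.2 leaves removal from treatment to the investigator's judgment. These narrow the gap, but inside it none is a mandatory stop.
- **The rule names AST or ALT.** If only one enzyme was raised at baseline, the other can arguably still satisfy the limb.
- **The qualifier was deliberate.** Amendment 6 introduced it. That explains the condition but not the missing alternative for a raised baseline.

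A reader might go further and infer that, with a raised baseline, the enzyme limb drops out and TBL and ALP alone force a stop. The text does not support this. The limb speaks of increased AST or ALT, the last condition refers to a combination of abnormalities, and Appendix B describes concurrent AST/ALT and TBL elevation.

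A reader might also infer that the 24-hour SAE report is owed only with a normal baseline. On its face, the Appendix B summary requires it at any baseline. Beyond that, "Other events of hepatotoxicity and potential DILI should be reported as serious adverse events if they meet the criteria" for seriousness in Section 9.2.1.

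**Conclusion.** The point holds as a narrow conflict between two sections. As written, 6.1.3.2 gives no mandatory combined stop on an enzyme that was at or above ULN at baseline, whereas the Appendix B criteria would be met by the same values. It would be too strong to call the rule wholly indeterminate or these subjects unprotected: close observation applies throughout the gap, and the any-one list takes over once values become more extreme or symptoms appear.

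Severity is minor. No endpoint, analysis set or planned analysis is affected. How many subjects have a raised baseline is not stated in the documents, so the number exposed cannot be estimated. The conclusion rests on reading the baseline condition as it is worded and on no other apparent cause being present.

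**What to change.** In Protocol 6.1.3.2, state the AST/ALT limb as above 3x ULN regardless of baseline. Leave TBL at least 2x ULN, ALP below 2x ULN and no other apparent cause unchanged. This matches Appendix B and gives one answer for every eligible subject. If the sponsor prefers to keep a baseline condition, it should add an explicit limb for baseline at or above ULN and use the same wording in Appendix B.

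The edit is one line, but it needs a protocol amendment with investigator agreement and IEC/IRB approval (Section 12.1) at about 50 centers (Section 3.2). The documents do not show whether another amendment is planned; the SAP of 26 May 2018 still works from Amendment 6. The clinical cost is a few more precautionary stops in subjects with a raised baseline, since at 2.5x ULN a rise just over 1.2-fold meets the limb. The TBL, ALP and no-other-cause conditions limit how often that would lead to a stop.

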6.2 Product Complaints, Including Device Complaints

A product complaint is defined as any written, electronic or oral communication that alleges deficiencies related to the identity, quality, durability, reliability, safety, effectiveness, or performance of a drug(s) or device(s) after it is released for distribution to market or clinic by either Amgen or by distributors and partners for whom Amgen manufactures the material. **This includes drug(s) or device(s) provisioned and/or repackaged/modified by Amgen. Drug(s) or device(s) includes investigational product.**

Concerns or irregularities about the packaging, appearance or usage of the prefilled AI/Pen or personal injector or other Amgen provided, protocol-required product in this study are to be reported to Amgen within 24 hours of discovery or notification of the concern or irregularity. Should any such concerns or irregularities occur please do not use the IP until Amgen confirms that it is permissible to use.

Medical supplies (eg, syringes, sterile needles, alcohol prep pads), that are commercially available are not usually provided or reimbursed by Amgen (except, for example, if required by local regulation). The Investigator will be responsible for obtaining supplies of these devices.

Examples of potential product complaints that need to be reported to Amgen include, but are not limited to:

- broken container or cracked container
- misuse of the AI/pen **or personal injector** due to misunderstanding of the IFU or error on the part of the user, or other inability to appropriately use the product (eg, due to malfunction of the AI/Pen or personal injector)
- missing labels, illegible labels, incorrect labels, and/or suspect labels
- change in IP appearance, for example color change or visible presence of foreign material
- unexpected quantity or volume, for example number of tablets or amount of fluid in the prefilled AI/Pen or personal injector cartridge
- evidence of tampering or stolen material

If possible, please have the IP or other Amgen provided protocol-required suspect product available for examination when making a product complaint. Maintain IP or other Amgen provided protocol-required suspect product at appropriate storage conditions until further instructions are received from Amgen.

The investigator is responsible for ensuring that all product or device complaints observed by the investigator or reported by the subject that occur after signing of the informed consent through 30 days after the last dose of IP or EOS, whichever is later, are reported to Amgen within 24 hours of discovery or notification of the product complaint.

For more details regarding the identification and reporting of product and device complaints, refer to the IPIM.

